12.3 Data Analysis and Coordination

Data analysis will be conducted with the help of the Yale Center for Analytic Sciences (YCAS) and will be performed using SAS v9.4 (SAS Institute, Cary, NC). Analysis of feasibility will be primarily descriptive. Numeric summaries including frequencies for categorical outcomes and means, medians, standard deviations and interquartile ranges for continuous feasibility outcomes will be presented. Graphical summaries will be used to describe distributions of outcomes and relations of outcomes with baseline characteristics. 95% confidence intervals for means and proportions will be estimated to describe uncertainty from sampling variation for feasibility outcomes.

The research team seeks to broadly disseminate the study results through publication in peer-reviewed journals and presentations at national meetings to share and demonstrate the findings and the lessons learned from this project. We plan to present at conferences such as the Gerontological Society of America annual meeting, the American Geriatrics Society annual meeting, and the National Association of Adult Protective Services annual meeting.

In accordance with the National Institutes of Health (NIH) policy to promote broad and responsible dissemination of information from NIH-funded clinical trials, we are registered VOICES trial on ClinicalTrials.gov (<https://clinicaltrials.gov/ct2/show/NCT03834870>). In addition, we will submit the VOICES trial results information to ClinicalTrials.gov.

The informed consent documents for the VOICES trial will include a specific statement that states the posting of clinical trial information at ClinicalTrials.gov and the trial number.

13. Statistical Considerations: Describe the statistical analyses that support the study design.

VOICES-C and D:

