Data collection instruments for usability are tools that help us analyze the design, implementation, and integration process. Usability data analysis will include percentage of successfully completed tasks; number and types of errors; time to successfully perform a particular task; user satisfaction ratings; and verbal and written feedback from the sessions. Quantitative data will be analyzed as numerical indicators and summarized using common descriptive statistics appropriate for discrete and continuous data. Non-numerical indicators will be analyzed using qualitative methods. Key results will be used to 1. Modify the VOICES tool to make it more usable and acceptable in terms of system's design; and 2. Normalize VOICES by reducing process and structural problems. We will conduct data analysis by using Camtasia 2®, a package that allows simultaneous video recording, user screen capture, note-taking, and participant survey. Key usability measures will include both qualitative and quantitative outcome measures. These include effectiveness (i.e., how well a system does what it is supposed to do), efficiency (i.e., the way a system supports users), and satisfaction (i.e., subjective responses from users about the system).

VOICES Feasibility Study:

Sample size calculations were performed using PASS v2012. The objective of this study is to evaluate markers of feasibility rather than to determine the efficacy of VOICES. The sample size was therefore determined based on the practical considerations of time and availability of subjects as well as the precision by which feasibility parameters will be estimated. We estimate EM prevalence to range from 7% to 12% among adults age 60 and above since the reported numbers in literature were for ages 65 and above. In addition, if we also assume that 20% of them may not participate in the study based on cognitive ability, then we can expect the EM prevalence in our eligible sample to range from 6% to 9.6%.

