If we also exclude subjects with clear signs of EM (1 in 24) 5%, as they will be immediately identified and reported by health care provider, then we are left with EM prevalence estimation of 5.7% - 9.12%. A sample size of eight hundred subjects (N=800) should thus result in 45-72 adults from whom we can estimate the proportions who change their self-identification response and who are ready to self-disclose after using VOICES. This will be a sufficient size to estimate a 95% confidence interval around a proportion with a width of no greater than 0.3. A sample size of 800 will provide a precision of +/- 0.14 standard deviations for the 95% confidence interval around a mean for continuous feasibility outcomes (e.g. acceptability, time to completion). This sample size will also produce precision of no worse than +/- 14% in the estimation of a 95% confidence interval around a proportion for dichotomous feasibility outcomes (e.g. demand, implementation).

SECTION II: RESEARCH INVOLVING DRUGS, BIOLOGICS, RADIOTRACERS, PLACEBOS AND DEVICES

If this section (or one of its parts, A or B) is not applicable, check off N/A and delete the rest of the section.

A. RADIOTRACERS **N/A**

B. DRUGS/BIOLOGICS **N/A**

B. DEVICES **N/A**

SECTION III: RECRUITMENT/CONSENT AND ASSENT PROCEDURES

1. Targeted Enrollment: Give the number of subjects:

- Targeted for enrollment at Yale for this protocol: 800
- If this is a multi-site study, give the total number of subjects targeted across all sites:

2. Indicate recruitment methods below. Attach copies of any recruitment materials that will be used.

VOICES Feasibility Study:

 Flyers	 Internet/web postings	 Radio
 Posters	 Mass email solicitation	 Telephone
 Letter	 Departmental/Center website	 Television
 Medical record review*	 Departmental/Center research boards	 Newspaper
 Departmental/Center newsletters	 Web-based clinical trial registries	 Clinicaltrials.gov
 YCCI Recruitment database	 Social Media (Twitter/Facebook):	

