7. ANALYTIC PLAN
 - 7.1. Analysis of Primary Outcome
 - 7.2. Analysis of Other Pre-Specified Outcome Measures

REFERENCES

STUDY SUMMARY (revised 3/1/2023)

Title	Virtual cOaching in making Informed Choices on Elder Mistreatment Self-Disclosure (VOICES)
Study Design	The design is a single arm trial to develop the digital intervention and conduct a feasibility study across five important areas including: acceptability, demand, implementation, practicality, and limited efficacy.
Study Duration	16 months
Trial Sites	Yale-New Haven Hospital Emergency Department on the Saint Raphael's Campus (YNHH-ED-SRC).
Objective	The purpose of this study is to evaluate the feasibility of using VOICES Elder Mistreatment (EM) intervention in the emergency department to detect cases of EM.
Number of Subjects	Over the course of this project, we recruited 1002 participants.
Main Inclusion Criteria	Inclusion Criteria: (1) Age 60 years or older; (2) non-full trauma track upon arrival; (3) Alert and oriented to person, place and time; (4) AMT4=4; (5) Able to consent and communicate in English; and (6) Agrees and able to use the iPad; (7) Not in police custody
Intervention	Our intervention is innovative because it utilizes best practices, and innovations in the design and development of digital health to create the one of its kind VOICES EM Intervention. As an easy-to-use, user-friendly EA intervention that runs on tablets with the information and messages displayed on the screen and spoken through headphones for privacy. VOICES delivers content specifically designed to target three factors (attitudes, subjective norms, perception of control) while providing accurate education on EM and APS response and dispelling myths and stereotypes surrounding victimization. VOICES will address perceptions of control making it easy to self-report and ask for help. Another innovative feature of VOICES is the ability to deliver health information through the use of digital tools, multimedia, and digitally guided interviews to older adults to increase awareness of EM.
Duration of Intervention	One session 8.8 minutes on average
Primary Outcome	The primary outcomes are participation and usage. Participation will be determined by the number of patients enrolled in VOICES. Usage will be determined by the number of patients enrolled in the study that complete the VOICES tool.
Primary Analysis	Primary outcomes will be tabulated as counts and frequencies.

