6. SAMPLE SIZE

6.1 Sample Size Determination for the Primary Outcome

Given that VOICES is a new tool, we did not have the needed information to estimate a power analysis or judge an approach sample size to calculate a meaningful sensitivity analysis when planning for the study. However, based on the initial analysis of the relevant population and our sample size, we estimate VOICES will detect EM in 40 to 70 older adults. We will report the 95% confidence intervals with our finding of sensitivity.

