7.2 Analysis of Other Pre-Specified Outcomes

Acceptability: Participant satisfaction will be measured along multiple dimensions using post-use satisfaction survey with two 5-point Likert response set scales, developed by the research team. Scale 1: Likert scale 1-5, where 1= Very Dissatisfied, and 5= Very Satisfied Scale 2: Likert scale 1-5, where 1= Strongly Disagree, and 5= Strongly Agree. The means and standard deviations will be reported.

Demand: Demand will be assessed through examining how likely will VOICES be used by patients. To do this, the size of target population of EM victims in the ED will be measured by the % of the patients who self-identified with elder mistreatment and the % who receive the Brief Negotiation Interview (BNI) portion of VOICES. Counts of participants will be reported.

Practicality: Practicality will be assessed by observing the ease of VOICES use by patients. To do this, a series of steps will be watched to determine the efficiency of implementation measured by the average time (1) to consent & orient participants to the tool and (2) needed to complete VOICES documented by the Research Assistant; and (3) patients perceived time of VOICES as measured on post-survey. Each of these will be reported as part of the overall outcome. The means and standard deviations will be reported.

Efficacy of the Educational Material: To understand the efficacy of VOICES in this pilot, we will look at how many participants changed their self-identification response after completing the educational component. Counts of participants will be reported.

Efficacy of the Brief Negotiation Interview: We will look at how many patients changed their readiness to identify and readiness to disclose after completing the Brief Negotiation Interview (BNI). Counts of participants will be reported.

Efficacy of Self-Identification on Self-Disclosure: We will explore whether self-identification impacts likelihood of self-disclosure. Counts of participants who change willingness to disclose among those that self-identify will be reported.

Accuracy: To understand the accuracy of the VOICES tool, a preliminary evaluation of the accuracy of VOICES as a screening tool in correctly classifying EM cases that were positive based on social worker assessment, and those referred to Adult Protective Services (APS). The percent correct classification will be reported.

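### Protocol section 13 gives the 95% CI precision for a mean at N=800 as ±0.14 SD; the half-width is ±0.07 SD, and 0.14 SD is the full width

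*Protocol*

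**What the plan says.** Protocol section 13 (Statistical Considerations, VOICES Feasibility Study) says that the sample size rests on "practical considerations of time and availability of subjects as well as the precision by which feasibility parameters will be estimated". It then gives three precision statements in one paragraph:

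- For the 45 to 72 participants expected to have experienced mistreatment, the sample allows "a 95% confidence interval around a proportion with a width of no greater than 0.3".
- For continuous feasibility outcomes, with acceptability and time to completion as examples: "A sample size of 800 will provide a precision of +/- 0.14 standard deviations for the 95% confidence interval around a mean".
- For dichotomous feasibility outcomes, with demand and implementation as examples: "precision of no worse than +/- 14% in the estimation of a 95% confidence interval around a proportion".

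Protocol section 12.3 commits to the matching intervals: "95% confidence intervals for means and proportions will be estimated to describe uncertainty from sampling variation for feasibility outcomes". The same commitment appears in the Aim 2 data analysis text of the research plan.

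The SAP does not carry the 0.14 SD figure. Its section 6.1 says of the planning stage that "we did not have the needed information to estimate a power analysis". Its Study Summary reports the final count: "Over the course of this project, we recruited 1002 participants". For acceptability and for the time measures, SAP section 7.2 says only: "The means and standard deviations will be reported".

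**The concern.** Precision expressed in SD units depends only on the sample size and the confidence level, and the sentence on means supplies both. The figure can therefore be checked directly, and it does not follow from 800. The ± sign denotes a half-width, and the sentence states what the sample will deliver rather than setting an upper limit.

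The protocol names precision as one of the grounds for the sample size, so the figure is part of the stated justification for 800. A reader who checks it will find that the claimed precision needs about a quarter of that number, which makes the target look unexplained. Anyone who reuses the statement to plan the larger study the protocol anticipates would understate by half the precision that a given sample gives.

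**Working it through.** **Inputs**

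- N = 800: Protocol section 13, and the enrolment target in Section III, item 1.
- Two-sided 95% interval, z = 1.96: the intervals planned in Protocol section 12.3, and the ± in the statement itself.
- SD = 1, because precision is expressed in SD units.
- One group: Protocol section 12 says there is no control group, and SAP section 3 describes a single-arm design. No clustering or design effect is stated.

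**Step 1. Half-width at the planned N**

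Half-width = z/√N = 1.96/√800 = 1.96/28.284 = 0.0693 SD. With the t quantile on 799 degrees of freedom it is 0.0694 SD. The stated ±0.14 SD is not reproduced: 0.14/0.0693 = 2.02.

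**Step 2. Full width at the planned N**

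2 × 0.0693 = 0.1386 SD, which rounds to 0.14. The stated number equals the full width.

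**Step 3. The N that would give the stated half-width**

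N = (1.96/0.14)² = 14² = 196, or about 199 with the t quantile. 196/800 = 0.245, about a quarter of the target.

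**Step 4. Could another convention give ±0.14 SD at N = 800?**

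| Variant | Half-width (SD) |
|---|---|
| One-sided 95%, or 90% two-sided | 0.058 |
| 95% with 80% to 99% tolerance probability for an unknown SD | 0.071 to 0.073 |
| 95% with an assumed 20% loss (n = 640) | 0.077 |
| 99% | 0.091 |
| 99.9% | 0.116 |

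None reaches 0.14. A design effect of (0.14/0.0693)² ≈ 4.1 would be needed.

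**Step 5. At the number recruited**

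1.96/√1002 = 0.0619 SD.

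**Step 6. The neighbouring statements on proportions**

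- All participants, p = 0.5: 1.96 × √(0.25/800) = 0.0346, so at most about 3.5 percentage points (3.1 points at 1,002). The ±14% limit is therefore true but loose; it corresponds to n = (1.96 × 0.5/0.14)² = 49.
- Subgroup of 45, p = 0.5: full width 2 × 1.96 × √(0.25/45) = 0.292, inside the stated 0.3. This uses the Wald interval. Wilson gives 0.280. Exact Clopper-Pearson gives 0.305, marginally above. The protocol names the software but not the interval method. Where the paragraph means the whole interval, it uses the word width.

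**The case against.** The strongest objection is that nothing turns on the figure. It understates precision, so 800 is more than enough. The sample size also rests on time and availability of subjects, the analysis is mainly descriptive, and no test, decision rule or stopping rule uses 0.14 SD. Recruitment has finished at 1,002, the SAP omits the figure, and SAP section 7.2 plans no confidence intervals for the outcomes concerned. All of this stands, and it keeps the point minor. It does not make the sentence correct.

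A second objection concerns the origin. Because 800 is four times 200, a half-width calculated for about 200 participants gives the same 0.139 SD. At that size the worst-case full width for a proportion is also 0.139, which would fit the adjacent 14% too. At N = 800 the full width for a proportion is only 6.9 points. So a confusion of full width with half-width is one possible explanation, and a figure carried over from a smaller sample is another. The documents do not decide between them, and the finding does not need them to.

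Third, inferring the meaning of ± from the word width in a neighbouring sentence is weaker than the ordinary meaning of ±, which suffices alone; that neighbouring 0.3 limit also depends on the interval method. Fourth, the ±14% limit for proportions is worded as a bound and is true, so changing it is optional. Finally, 0.069 SD assumes that all 800 contribute data. Acceptability comes from a post-use survey and the protocol allows for non-completion, so a corrected statement should say so. An assumed 20% loss gives 0.077 SD, still far from 0.14.

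**Conclusion.** The concern holds. At N = 800 the 95% half-width for a mean is 0.069 SD, not 0.14 SD, an overstatement by a factor of 2. This assumes a single sample of independent participants, a two-sided 95% interval and complete data; none of the alternatives tried closes the gap. The error is conservative and minor: it is confined to one planning sentence, leaves 800 adequate, and affects no analysis or conclusion. The ±14% statement for proportions is loose, not wrong.

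**What to change.** In Protocol section 13, replace the sentence on means with wording such as: with complete data, 800 participants give a 95% confidence interval half-width of about 0.07 SD for continuous feasibility outcomes. Optionally, tighten the next sentence to a half-width of at most about 3.5 percentage points for dichotomous outcomes measured on all 800 participants. If the sample-size rationale is quoted in a report or reused to plan the follow-on study, use the corrected figures.

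The cost is one sentence of the protocol, or two adjacent sentences with the optional change. The SAP, conduct and analysis are unaffected.

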7. ANALYTIC PLAN
 - 7.1. Analysis of Primary Outcome
 - 7.2. Analysis of Other Pre-Specified Outcome Measures

REFERENCES

STUDY SUMMARY (revised 3/1/2023)

Title	Virtual cOaching in making Informed Choices on Elder Mistreatment Self-Disclosure (VOICES)
Study Design	The design is a single arm trial to develop the digital intervention and conduct a feasibility study across five important areas including: acceptability, demand, implementation, practicality, and limited efficacy.
Study Duration	16 months
Trial Sites	Yale-New Haven Hospital Emergency Department on the Saint Raphael's Campus (YNHH-ED-SRC).
Objective	The purpose of this study is to evaluate the feasibility of using VOICES Elder Mistreatment (EM) intervention in the emergency department to detect cases of EM.
Number of Subjects	Over the course of this project, we recruited 1002 participants.
Main Inclusion Criteria	Inclusion Criteria: (1) Age 60 years or older; (2) non-full trauma track upon arrival; (3) Alert and oriented to person, place and time; (4) AMT4=4; (5) Able to consent and communicate in English; and (6) Agrees and able to use the iPad; (7) Not in police custody
Intervention	Our intervention is innovative because it utilizes best practices, and innovations in the design and development of digital health to create the one of its kind VOICES EM Intervention. As an easy-to-use, user-friendly EA intervention that runs on tablets with the information and messages displayed on the screen and spoken through headphones for privacy. VOICES delivers content specifically designed to target three factors (attitudes, subjective norms, perception of control) while providing accurate education on EM and APS response and dispelling myths and stereotypes surrounding victimization. VOICES will address perceptions of control making it easy to self-report and ask for help. Another innovative feature of VOICES is the ability to deliver health information through the use of digital tools, multimedia, and digitally guided interviews to older adults to increase awareness of EM.
Duration of Intervention	One session 8.8 minutes on average
Primary Outcome	The primary outcomes are participation and usage. Participation will be determined by the number of patients enrolled in VOICES. Usage will be determined by the number of patients enrolled in the study that complete the VOICES tool.
Primary Analysis	Primary outcomes will be tabulated as counts and frequencies.
Other Pre-Specified Outcome Measures	
 1. Acceptability 2. Demand 3. Practicality 4. Efficacy of the Educational Material 5. Efficacy of the Brief Negotiation Interview 6. Efficacy of Self-Identification on Self-Disclosure 7. Accuracy

1. BACKGROUND

Elder mistreatment (EM) is a major public health problem with prevalence estimate ranges from 7.6% to 12.7% among older adults. EM causes serious adverse outcomes for its victims including injury, increased service utilization, mental distress and increased mortality. A major barrier in overcoming EM is the inability to accurately identify EM victims. It is estimated that only **1 in 24 cases** become known to authorities. This is problematic as older adults are not likely to report that they are being mistreated. To improve the screening for EM and promote self-disclosure we will study the Feasibility of Virtual cOaching in making Informed Choices on Elder Mistreatment Self-Disclosure (VOICES). The overarching aim of this project is to evaluate the feasibility of using VOICES Elder Mistreatment (EM) Intervention that runs on tablets and used by older adults to detect EM in emergency department (ED) settings. VOICES will be utilizing virtual coaching, interactive multimedia libraries (e.g., graphics, video clips, animations, etc.), techniques from electronic screening for intimate partner violence, and brief motivational interviewing designed to enhance identifying EM among older adults. This project includes developing new *screening framework*, as well as a study to examine the feasibility of this complex interventions in real-world settings.

2. AIMS

Aim 1. Feasibility Study: To conduct a feasibility study (N= 1002) examining the use of VOICES in a busy ED.

Aim 2. Exploratory Aim: To perform a preliminary evaluation of the accuracy of VOICES as a screening tool in correctly classifying EM cases that were referred to Adult Protective Services (APS).

3. STUDY DESIGN

The design is a single arm trial to develop the digital intervention and conduct a feasibility study across five important areas including: acceptability, demand, implementation, practicality, and limited efficacy. The primary outcomes are participation and usage. Participation will be determined by the number of patients enrolled in VOICES. Usage will be determined by the number of patients enrolled in the study that complete the VOICES tool. Over the course of this project, we recruited 1,002 subjects over 16 months.

4. OUTCOMES

The primary and Other Pre-Specified Outcome Measures are summarized in Table 1.

Table 1. Primary and Other Pre-Specified Outcome Measures		
Domain	Measure (P,O)	Source and Frequency
Implementation	Participation. Participation will be determined by the ratio of participants who are successfully enrolled to the total	Study enrollment records

	number of eligible patients. (P)	
	Usage. Usage will be determined by the number of consented participants enrolled in the study who used VOICES to completion (P)	VOICES tool completion records
Acceptability	Participant satisfaction measured using post-use satisfaction survey with two 5-point Likert response set scales, developed by the research team (O)	Self-report, once per participant
Demand	Measured by the % of the patients who self-identified with elder mistreatment and the % who receive the Brief Negotiation Interview (BNI) portion of VOICES.	Measured by VOICES tool, once per participant
	Average time to consent & orient participants to the tool (O)	RA measurement, once per participant
Practicality	Average time needed to complete VOICES (O)	RA measurement, once per participant
	Average time patients perceived time of VOICES	Self-report, once per participant
Efficacy of the Educational Material	Measured as % of participants that change their self-identification response after completing the educational component (O)	Measured by VOICES tool, once per participant
Efficacy of the Brief Negotiation Interview	Measured as % participants that change their self-identification response after completing the educational component (O)	Measured by VOICES tool, once per participant
Efficacy of Self-Identification on Self-Disclosure	Measured as % of patients who disclose among those who self-identified (O)	Measured by VOICES tool, once per participant
Accuracy	Measured as percent of classified EM cases that were positive based on social worker assessment, and those referred to Adult Protective Services (APS). (O)	Measured by the outcome of the social worker assessment and by the outcome APS evaluation.
EM: Elder Mistreatment; BNI: Brief Negotiation Interview; APS: Adult Protective Services		

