Demand	To what extent is VOICES likely to be used?	Size of target population of EM victims in the ED measured by % who screen positive for EM and % who receive the BNI portion of VOICES
Implementation	To what extent can VOICES be delivered to participants in the defined, but not fully controlled, context of the ED?	Degree of execution measured by % of potential participants approached who consent to participate in the pilot study Success of execution measured by # of participants who used the tool to completion and reasons for not completing the tool as reported on post-survey
Practicality	To what extent can VOICES be carried out with intended participants without outside intervention?	Efficiency of implementation measured by the average time (1) to consent & orient participants to the tool and (2) needed to complete VOICES documented by the RA; and (3) patients perceived time of VOICES as measured on post-survey Factors affecting implementation measured by the number and source of interruptions during participation documented by the RA; The number of participants who want their caregiver/family member present during study as documented by the RA Positive/Negative effects of VOICES measured by participants' perceptions of safety concerns vs. benefits as reported on post-survey
Limited Efficacy	Does VOICES show promise of being successful?	Observed trends in proportions of reported (1) portion of participants who change their self-identification response after completing the education (2) portion of participants who change readiness to disclose after completing the BNI (3) exploration of whether self-identification impacts likelihood of self-disclosure Effect-size estimation measured by change in the % of patients who disclose Potential sources of bias measured by (1) sample representativeness & (2) observed group differences of participants measured by demographic data determine through t-tests and chi-square analyses

Table 1: Planned Data Analyses and Interpretation

Data Management. Study data will be entered into the VOICES by the patients through direct use and by the RA through data entry. We will use VOICES Back-end for the study management needs.

SPECIFIC AIM 3: Exploratory Aim: To perform a preliminary evaluation of the accuracy of VOICES as a screening tool in correctly classifying EM cases that were referred to Adult Protective Services (APS).

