4.2 Other Pre-Specified Outcomes

Acceptability: Participant satisfaction will be measured along multiple dimensions using post-use satisfaction survey with two 5-point Likert response set scales, developed by the research team. Scale 1: Likert scale 1-5, where 1= Very Dissatisfied, and 5= Very Satisfied Scale 2: Likert scale 1-5, where 1= Strongly Disagree, and 5= Strongly Agree

Demand: Demand will be assessed through examining how likely will VOICES be used by patients. To do this, the size of target population of EM victims in the ED will be

measured by the % of the patients who self-identified with elder mistreatment and the % who receive the Brief Negotiation Interview (BNI) portion of VOICES.

Practicality: Practicality will be assessed by observing the ease of VOICES use by patients. To do this, a series of steps will be watched to determine the efficiency of implementation measured by the average time (1) to consent & orient participants to the tool and (2) needed to complete VOICES documented by the Research Assistant; and (3) patients perceived time of VOICES as measured on post-survey. Each of these will be reported as part of the overall outcome.

Efficacy of the Educational Material: To understand the efficacy of VOICES in this pilot, we will look at how many participants changed their self-identification response after completing the educational component.

Efficacy of the Brief Negotiation Interview: We will look at how many patients changed their readiness to identify and readiness to disclose after completing the Brief Negotiation Interview (BNI).

Efficacy of Self-Identification on Self-Disclosure: We will explore whether self-identification impacts likelihood of self-disclosure. Effect-size estimation measured by change in the % of patients who disclose among those who self-identified.

Accuracy: To understand the accuracy of the VOICES tool, a preliminary evaluation of the accuracy of VOICES as a screening tool in correctly classifying EM cases that were positive based on social worker assessment, and those referred to Adult Protective Services (APS). The percent correct classification will be reported.

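### The outcome for efficacy of the educational material counts any change in self-identification, with no direction, an unreconciled denominator and no described pre-education answer

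*SAP*

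**What the plan says.** The SAP states this outcome three times. Table 1 in section 4 reads "Measured as % of participants that change their self-identification response after completing the educational component". Section 4.2 says "we will look at how many participants changed their self-identification response after completing the educational component", and section 7.2 repeats this and adds only that counts will be given: "how many participants changed their self-identification response after completing the educational component. Counts of participants will be reported". None of the three states a direction or a subgroup. Section 7.2 has no denominator and no confidence interval for this item, whereas section 7.1 asks for both for the primary outcomes.

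Protocol Table 1 (Specific Aim 2, Limited Efficacy row) is worded in the same way: "portion of participants who change their self-identification response after completing the education". Protocol item 13, Statistical Considerations, ties the proportion to a smaller group. It expects 800 enrolled to yield "45-72 adults from whom we can estimate the proportions who change their self-identification response", and says this is enough for a 95% confidence interval no wider than 0.3.

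On direction of intent, the protocol's Research Plan says VOICES is built to help victims recognise their own mistreatment and then disclose it.

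**The concern.** An outcome labelled efficacy should separate movement towards the tool's goal from movement away from it. Undirected change does not. It adds together people who came to recognise mistreatment, people who withdrew an earlier yes, and people who simply answered inconsistently. With one arm, there is no comparison group against which to judge the total.

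The denominator matters because most participants are expected not to be victims, and for them no is the expected answer both times. A percentage over everyone enrolled would mainly reflect how rare mistreatment is, and the precision stated in protocol item 13 would not describe it.

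The SAP, revised 3/1/2023, already reports 1,002 recruited. If direction and denominator stay open, they could be settled after the responses have been seen.

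**Working it through.** **1. The protocol's own figure.** Item 13 starts from "We estimate EM prevalence to range from 7% to 12% among adults age 60 and above", removes 20% for cognitive ability (stated result 6% to 9.6%), then 5% for clear signs of mistreatment:

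- 6% x 0.95 = 5.7% and 9.6% x 0.95 = 9.12%, matching "then we are left with EM prevalence estimation of 5.7% - 9.12" per cent.
- 800 x 0.057 = 45.6 and 800 x 0.0912 = 72.96, truncated to 45 and 72.
- Wald width at p = 0.5 is 2 x 1.96 x sqrt(0.25/n): 0.292 at n = 45 and 0.231 at n = 72.

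The stated range and the limit of 0.3 both reproduce. Two minor caveats apply. The lower end uses 7% x 0.8 = 5.6% rounded up to 6%; unrounded, it is 5.32%, or 42.6 cases. The Clopper-Pearson width at n = 45 is 0.305. The sizing therefore clearly rests on expected cases, not on all 800.

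**2. Direction.** The documents give no expected rate of change, so these counts are assumptions, set against the SAP's 1,002.

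| No to yes | Yes to no | Change as worded | Net shift towards yes |
|---|---|---|---|
| 20 | 0 | 20/1002 = 2.0% | +2.0% |
| 10 | 10 | 20/1002 = 2.0% | 0.0% |
| 0 | 20 | 20/1002 = 2.0% | -2.0% |

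Over 57 expected cases (1002 x 0.057 = 57.1), the change figure is 20/57 = 35.1% in all three rows, while the net shift is +35.1%, 0 and -35.1%. Changing the denominator does not cure the missing direction.

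**3. Denominator.** The same count over all participants, instead of over expected cases, shrinks by 1/0.0912 = 11.0 to 1/0.057 = 17.5. For illustration, assume about half of 57 expected cases move from no to yes. This gives 28/57 = 49.1% (Wilson 95% interval 36.6 to 61.7) on that group, and 28/1002 = 2.8% (1.9 to 4.0) on everyone.

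**4. Precision after the repair.** At 1,002 and the same prevalence, expected cases number about 57 to 91 (1002 x 0.057 = 57.1; 1002 x 0.0912 = 91.4), with Wald widths of 0.260 to 0.205. A no-to-yes proportion uses only those who first answered no, so its base is smaller. The worst-case Wald width stays within 0.3 while that base is at least (1.96/0.3)^2 = 42.7, that is 43 people.

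**5. Is there a before reading?** A change needs two answers. The Screening/Data Collection Description in the protocol describes the education and the screen, with the self-identification question asked afterwards. It describes no such question before the education. The source column of SAP Table 1 gives a single reading per participant for this row. The exact question wording was left to Aim 1, and the flow chart is not shown in the text available, so whether a before reading exists cannot be settled from the documents.

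**The case against.** The best defence is that the SAP is silent, not wrong. A reader might infer a rule that counts change in either direction, among all 1,002, as success. The documents state no such rule: they never say either direction, all participants or success for this outcome, and the tool's purpose makes no-to-yes the natural intention. That stands as a reading of intent. It does not rescue the wording, because an analyst who counts changed responses as written will include both directions.

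A reader might also infer that the SAP departs from the protocol. It does not depart from the protocol's outcome table, which is just as loose. The inconsistency is between that table and item 13 within the protocol, and the SAP inherits it.

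A third tempting inference is that a screen-negative participant who moves to yes is an error to be kept out of efficacy. The protocol's section on minimizing risks provides for patients whom the tool fails to identify but who wish to disclose. Such a person may be a victim whom the education helped. For the same reason, screen-positive is only a proxy for the expected cases in item 13.

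Finally, this is a non-primary outcome in a descriptive feasibility study. No test or decision threshold depends on it, and the documents tie no design input of the later effectiveness study to it. The protocol also plans 95% intervals for proportions in general. These points limit the seriousness. They do not supply a direction or a denominator.

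**Conclusion.** The point holds. As worded in SAP Table 1, 4.2 and 7.2 and in protocol Table 1, the outcome gives the same result for benefit, no net effect and harm. That follows from the wording and does not depend on the assumed counts, which only illustrate it. The denominator is unreconciled between protocol item 13 and the two outcome tables, and SAP 7.2 does not settle it. At the protocol's prevalence of 5.7% to 9.12%, the choice alters the reported percentage by a factor of about 11 to 18 for a given count. It is also unconfirmed that a pre-education answer exists. This should be corrected before the result is reported as efficacy. It does not affect the primary outcomes of participation and usage.

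**What to change.** - **Confirm the data first.** Establish whether the tool records a self-identification answer before the education, and describe both readings in the SAP. If there is none, state that the outcome cannot be computed and drop it.
- **Direction.** In SAP Table 1, 4.2 and 7.2, define the efficacy measure as no-to-yes and report yes-to-no separately.
- **Table and denominators.** Report the paired before/after table (no-no, no-yes, yes-no, yes-yes). Give no-to-yes among those who first answered no, and yes-to-no among those who first answered yes, each with numerator, denominator and 95% confidence interval.
- **Groups.** Present these overall and by EASI-sa screen status. Name the screen-positive group as a proxy for the expected cases in protocol item 13. Show screen-negative no-to-yes changes in their own row, without labelling them as outside efficacy.

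If both answers are recorded, the cost is revised wording in three places and one cross-tabulation. The downside is smaller bases, wider intervals and a less favourable figure than any change would give.
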